Accordingly, in this proposed study, we will determine if an individually tailored diet and PA enhancement program (TDPA), as compared to standard care controls (SC), can improve mobility (six minute walk, 6MW), physical activity (PA), and neuropathy measured using the IENFD. To our knowledge, no randomized controlled intervention trial has been directed toward actually reducing the progression of peripheral neuropathy, as well as determining the effect of this reduction on key factors such as mobility function and PA. The study will be performed at two sites – the Baltimore VAMC/University of Maryland and the Ann Arbor VAMC/University of Michigan and will leverage the strengths of both institutions (senior VA investigators and GRECC Directors at both sites) to increase the diversity and size of the participant recruitment sources and resources available to the study.

While other interventions, for example glucose-regulating medications, may affect mobility and neuropathy progression in patients with IGT, these approaches are costly and fail to address intrinsic problems in the patient's lifestyle. At present we do not know if a lifestyle intervention as proposed in this study will be effective, because such an intervention has never been tested in a randomized study. This is a fundamental question that needs to be answered. In this study we will use a home-based program that can be used within the community and therefore can be used by the majority of patients with IGR.

This study is novel and timely in that it will: 1) test the efficacy of a TDPA protocol in preventing the progression of neuropathy and improving mobility function and PA in participants with IGR; and 2) explore if these processes are associated with changes in metabolic state of the trial participant.

(2) Endpoints and Hypotheses

Endpoints and hypotheses are prioritized according to their importance in the present proposal as the key endpoints (primary and then secondary) and those of lesser importance (tertiary and exploratory/mechanistic).

Endpoints

6 month

12 month

Primary	6 minute walk (6MW)	
Secondary	Physical activity (PA)	IENFD
Tertiary		6MW, PA

Primary Hypothesis (6MW at 6 months): Compared to IGR participants advised to follow the current standard care recommendations on diet and PA (Standard Care or “SC”), IGR participants undergoing TDPA enhancement program will show greater improvement in the 6 Minute Walk (6MW) at 6 months.

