Participants will be allocated to TDPA or SC groups according to a minimization scheme. Minimization maintains balance in group distributions of a number of key variables by assigning subjects to either TDPA or SC group based on: age strata (30-40, 41-50, 51-60, 61-75), gender (male vs female), and BMI (less than 30, 30-40, >40). Since the number of stratification cells generated by these factors is large, the use of minimization techniques for subject assignment is especially suitable (78). Minimization stipulates that the next subject to enter the trial is assigned to a group with a probability greater than 0.5 in favor of the treatment that minimizes group imbalance on a particular variable. This minimization of strata imbalance between the training and control groups also reduces confounding of the outcome with prognostic factors, similar to stratified randomization. Operationally, after completing baseline testing, minimization strata for each participant are entered into a computer program which then generates the group assignment for that participant. We have used minimization in a number of controlled exercise studies and it appears to be a reasonable alternative to randomization when key confounders must be controlled and a relatively small sample is anticipated for recruitment.

Sample size calculation: We consider three outcomes: 1) Primary endpoint: 6MW at 6 months. 2) Secondary endpoint: IENFD at 12 months 3) Secondary endpoint: PA at 6 months.

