- 2) **Cutaneous Innervation Laboratory Data Integrity and Quality Control Procedures:** Each punch biopsy specimen is given a unique number and placed in a -20 deg freezer. Each step in the processing, including quality control data and precise location of each punch biopsy and section are recorded in a secure on-line password protected database. This database is backed up nightly. Intraepidermal nerve fiber density measurements are performed using established criteria (81). **See Appendix for specific counting methodology (81).** For each study, approximately 5% of samples are randomly selected for blinded recount to ensure adequate test retest reliability. The laboratory has demonstrated excellent intra and inter observer reliability, with intraclass correlation coefficients of greater than 95% and relative intra-trial variability of approximately 10% (32). Additionally, the laboratory participates in a multicenter quality control program in cooperation the laboratories at Johns Hopkins University, Rochester University and the Cleveland Clinic. Quarterly, one laboratory sends sections to another for independent analysis.
- 3) **Nerve Conduction Studies (NCS):** will be used to measure neuropathy progression (see Current Status, Endpoint Measures of Neuropathy for rational). NCS will be performed on the left side with the lower limb maintained at 32°C and the upper limb at 33°C (82). The amplitudes of the sural sensory, peroneal motor, tibial motor, radial sensory, and ulnar sensory and motor nerves and their respective distal and long latencies, and conduction velocities are obtained. Data will be used from individual measurements and using a mega score of combined variables. The electrophysiology personnel at both sites have been trained by [name] and nerve conduction results from Ann Arbor will be faxed to Batimore for reading by [name] group. This will ensure reliability and uniformity of electrodiagnostic studies.

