5) Strategies for multiple inferences: The analysis involves several hypotheses tests, thereby requiring a strategy to control the alpha level. We will give higher priority to the primary hypothesis so that the outcomes of tests of mechanism hypotheses will not be given the same strength of interpretation. Overall significance levels will be controlled using the probabilistic inequalities (e.g. Bonferroni or Sidak's methods), adjusted confidence limits (e.g. Tukey), methods based on resampling (109) or other appropriate multiple comparison adjustment methods (7).

Hypothesis testing plan

For the purposes of hypothesis testing, specific key primary and secondary variables, based on previous pilot data have been identified.

Endpoints	6 month	12 month
Primary	6 minute walk (6MW)	
Secondary	Physical activity (PA)	IENFD
Tertiary		6MW, PA

Primary Hypothesis (6MW at 6 months): Compared to IGR participants advised to follow the current standard care recommendations on diet and PA (Standard Care or "SC"), IGR participants undergoing TDPA enhancement program will show greater improvement in the 6 Minute Walk (6MW) at 6 months.

Secondary Hypothesis 1 (PA at 6 months): At 6 months and compared to SC, TDPA participants will show greater improvement in self-reported PA.

For the Primary Hypothesis and Secondary hypothesis 1 that address the 6-month 6MW and PA intervention effect, the goal is to determine whether there is a group (TDPA versus SC) difference in 6-month improvement. A regression model will be used to test these hypotheses

controlling for the minimization variables and baseline outcomes (BA=outcome at baseline; GEN=Gender; BMI=Body Mass Index, Age=Age, GRP=intervention group):
Outcome at 6 months= BA+GEN+BMI+AGE+GRP

Secondary Hypothesis 2 (IEFND at 12 months): At 12 months and compared to SC, TDPA participants will show better maintenance of IEFND.

A similar strategy will be used to test for the 12 month intervention effect.

Outcome at 12 months= BA+GEN+BMI+AGE+GRP

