We will rely on regression models to study multivariate relationships. These hypotheses will be addressed by examining the extent to which change in one of these measures relates to each other when controlling for other factors. Models can utilize outcome measurements at all time points (baseline, 6 months, and 12 months). We can also consider a number of measurements as contributing factors, i.e. covariates. For longitudinal data, models of the following type will be considered: (VS=Variables used in minimization; BA=outcome at Baseline; GRP=intervention group; COV= one or more covariates; TIME= time variable; *=interaction between variables):
Outcome at 6 and 12 months = VS + BA + GRP + COV + GRP*TIME + COV*TIME

The key aspects of this model in the context of our tertiary hypotheses are interactions GRP*TIME and COV*TIME, and the magnitude and significance of these interaction effects provide insight into mechanisms underlying study group differences. The remaining terms are used in the model to reflect study design and adjust for baseline values. The following methods will be considered particularly when analyzing longitudinal data for post-intervention hypotheses: LME models for continuous variables with normally distributed residuals); GLMM (111), and SAS PROC/GLMMIX (112). Both of these methods allow for unbalanced data, time-varying covariates, and structured covariance matrices. For the 12 month outcome, the model can take into account repeated measures and as such will be developed in the framework of LME or GLMM.

These exploratory analyses will not provide a definitive mechanism underlying changes in neuropathy progression, mobility function, or PA but we will be able to determine which variables are more strongly correlated and potentially more physiologically related. Our sample size of 64 per group (which should be achievable because we will recruit more people based on drop-out, as previously discussed) allows

us to detect effects of variables and/or their interactions as low as 5-6% of the variance explained over and above other predictors with alpha=0.05 and power of 80%.

Table 5: Summary of Variables

Variable	Type	Time		
		Baseline	6 months	12 months
Age, Gender, BMI	Minimization variables			
6MW	Dependent (Primary)	X	X	X
IENFD	Dependent (Secondary)	X		X
CHAMPS	Dependent (Secondary)	X	X	X
Measures of progression: MDNS	Covariates	X	X	X
Electrophysiological measures of progression: NCS	Covariates	X	X	X

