7) Move Program: We carefully considered adapting the nationwide VA Managing Overweight and/or Obesity for Veterans Everywhere Program (MOVE) as the main intervention but favored our tailored behavior change program with which we have extensive experience. Our rationale is that the MOVE program:

i) is primarily focused on diet and weight control and less on PA, the latter a key outcome in the present study.

ii) has less intensive contact with trainers than in TDPA.

iii) is focused on improving aerobic function and strength, whereas TDPA is focused on improving walking and balance, two key deficits in IGT-neuropathy in our pilot data.

iv) advises that the participant reach relatively high RPE (Rated Perceived Exertion) levels (up to 16 out of 20), which may require formal stress testing for safety, thereby requiring physician involvement, while the goal peak recommended TDPA RPE is 13. At week 13 and thereafter, the goal MOVE RPE is 13, the same as TDPA.

v) advises attendance at group diet seminars (at Level 2) whereas TDPA is individualized and home-based.

vi) is based conceptually on stage of readiness and self-efficacy whereas TDPA is based on a broader behavioral model, with the examination of perceived behavioral control (barriers), attitudes toward PA, and social support, as well as self-efficacy. This broader theoretical framework allows the trainers to tailor advice on additional important factors found to influence PA.

vii) is otherwise consistent with the TDPA exercise frequency and duration.

(2) Resources

Neuro-electrodiagnostics Laboratory (Baltimore and Ann Arbor): Both laboratories are equipped to perform nerve conduction and autonomic studies. The Baltimore Laboratory consists of 4 new Teca Synergy electromyography machines. The laboratory is managed by a senior electrophysiology technician. The Ann Arbor VAMC laboratory is staffed by a senior electrophysiology technician trained by [name]. [name] will oversee the quality control on the electrodiagnostic studies at both sites.

Mobility and Exercise Testing: In Baltimore, participants will be tested in the GCRC and Human Motor Performance Laboratory (see letter from [name] and [name]), and in Ann Arbor in the clinical center of the VA GRECC and Mobility Research Laboratory.

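### Site is in no allocation list and no endpoint model of this two-site trial; a prespecified SITE term is a cheap, optional improvement of small and conditional benefit

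*Combined protocol and SAP*

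**What the plan says.** The introduction states that "The study will be performed at two sites", Baltimore and Ann Arbor. The walk is tested locally: "In Baltimore, participants will be tested in the GCRC and Human Motor Performance Laboratory", and in Ann Arbor in that site's own clinical center and mobility laboratory (Resources).

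- **Allocation, Methodology (Minimization Screen):** the factors are "age strata (30-40, 41-50, 51-60, 61-75), gender (male vs female), and BMI (less than 30, 30-40, >40").
- **Allocation, Human Subjects Involvement and Characteristics:** age, gender, BMI and time from diagnosis of IGR.
- **Allocation, limitations rationale, item 6:** age, gender and BMI are the chosen factors. Time since diagnosis of diabetes is among those considered but not chosen, because the number of factors was limited.
- **Primary and first secondary hypotheses (Hypothesis testing plan):** "Outcome at 6 months= BA+GEN+BMI+AGE+GRP", described as "controlling for the minimization variables and baseline outcomes".
- **Second secondary hypothesis:** "Outcome at 12 months= BA+GEN+BMI+AGE+GRP".
- **Longitudinal models (Additional data analyses):** these contain "VS=Variables used in minimization" and an open covariate term, COV.
- **Table 5:** age, gender and BMI are the minimization variables. No row names site.

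Site is in none of these lists. No section gives an expected between-site difference, a planned split of participants by site, or a statement that the minimization program runs separately at each site.

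**The concern.** With two recruiting and testing centers, site is an obvious candidate covariate. If outcomes still differ by site after baseline adjustment, a model without site leaves that difference in the error term. If site is not an allocation factor either, the arms can differ by chance in their site mix, and the estimate is not corrected for it. The plan does attend to site uniformity elsewhere: for nerve conduction it adds common training and central reading, saying "This will ensure reliability and uniformity of electrodiagnostic studies". What is at stake is a little precision and a correction for chance imbalance, not the validity of the comparison.

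A second, separate matter is that the allocation lists disagree on time from diagnosis. Because the model is said to control for the minimization variables, its content depends on which list is true. This adds no weight to the site point.

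**Working it through.** **Inputs.** From the sample size table: adjusted SD 97, difference 50, 64 per group, two-sided alpha 0.05 (the table gives no unit for 6MW). Assumed, because the documents are silent: D, the between-site difference in baseline-adjusted 6MW, in the same unit as the SD; the share of participants at one site, q; one minimization scheme pooled across sites; and that 97 is a total SD including between-site variation (its source study was multicenter).

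**The plan's own figure.** An effect size of 0.50 gives 64 per group by t-test. The tabled 0.51 gives 62, and 50/97 = 0.5155 gives 61. So 64 is reproduced or slightly conservative. At 64 per group with 50/97, noncentral-t power (126 df) is 82.5%.

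**Adding SITE.**

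- Within-site SD = √(97² − q(1−q)D²). For q = 0.5 and D = 50: √(9409 − 625) = 93.7.
- The chance difference d between arms in site share has SD √(0.25 × 2/64) = 0.088. Simulated minimization on age, gender and BMI, with assumed strata distributions, gave 0.087 to 0.091.
- Imbalance multiplies the variance by 1/(1 − r²), with r = 0.5d/√(q(1−q)). Power (125 df) is averaged over d.

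| D | Power with SITE, equal sites | Change from 82.5% (points) |
|---|---|---|
| 0 | 82.2% | −0.3 |
| 5 | 82.2% | −0.3 |
| 15 | 82.4% | −0.1 |
| 25 | 82.8% | +0.3 |
| 50 | 84.7% | +2.2 |

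Break-even is D = 17.3, and 17.3/97 = 0.18 SD. With a 70:30 split it is about 19. In equivalent participants out of 128, SITE costs about 1 at D=0 and gains about 1 at D=25 and 8 at D=50. A direct regression simulation of 6,000 trials agrees (without versus with SITE): 82.0% versus 81.7% at D=0, 82.6% versus 82.9% at D=25, 82.5% versus 84.9% at D=50.

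**If arms are balanced within site.** Then d is about 0, and at D=0 only one degree of freedom is lost: 82.48% to 82.47%.

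**Chance imbalance.** Ten percentage points of imbalance moves the estimate by 0.10 × D: 2.5 at D=25 and 5 at D=50. Against a standard error of 97 × √(2/64) = 17.1, that is 0.15 and 0.29 standard errors.

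**What D is plausible.** A stable site offset appears at baseline too. With an assumed baseline slope of 0.9 to 0.7, an offset of 50 leaves 50 × 0.1 = 5 to 50 × 0.3 = 15, which is below break-even.

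**Power without SITE on the other endpoints.** PA (difference 500, SD 1000, 64 per group): 80.1%. IENFD (difference 1.0, SD 2.2): about 72% at 64 per group and 64% at the stated 53.

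**The case against.** The strongest reply is that the gain is unproven and of uncertain sign. The power change is under 0.5 points either way up to D=25, and after baseline adjustment a stable offset could well leave a D at which SITE loses slightly. Other uncertainty is much larger. If the SD of 97 came from the 40 paired walks mentioned for the earlier cohort (an assumption), its 95% interval is about 79 to 125, and power at 64 per group runs from about 94% to 61%. The walk protocol is also standardized, with a measured course, scripted instructions and no encouragement. Skin biopsies have a described laboratory with blinded recounts and cross-laboratory checks, and PA is a questionnaire. All of this stands, and it keeps the point optional.

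The plan also has some flexibility. COV could admit site to the exploratory longitudinal models, and the general analytic plan includes residual checks for systematic departures. Neither prespecifies site for the primary model.

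A reader might infer from the separate laboratories, or from central reading of nerve conduction, that the sites do differ on the walk. The documents do not show this. Nerve conduction is listed as a covariate, and no section reports a between-site difference for any endpoint.

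**Conclusion.** The omission is real and its consequence is small. A reader might conclude that leaving site out biases the group comparison or inflates type I error. It does neither: nothing in the documents makes site an allocation factor, and the model already adjusts for baseline. Nor can a material power gain be claimed. Under the stated assumptions the effect runs from −0.3 points at D=0 to about +2 at D=50. The latter is best read as an upper bound, because a residual site difference of 50 equals the whole target effect. The cost at D=0 depends on pooled allocation and nearly vanishes if the scheme balances arms within site, which the documents leave open.

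The case for SITE is therefore a small possible loss set against correction for whatever imbalance occurs and for any residual site difference. It does not address a site-by-treatment effect.

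Planned power of 80% is met without SITE for 6MW and PA only. The IENFD shortfall is a separate matter that SITE does not repair.

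The conflict over time from diagnosis is a genuine inconsistency, with the Human Subjects section as the outlier.

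**What to change.** Before unblinding, consider prespecifying SITE as a fixed effect, `Outcome = BA + GEN + BMI + AGE + SITE + GRP`, in the 6-month and 12-month models, and naming it in the repeated-measures models rather than leaving it to COV. State whether the minimization runs per site or pooled. Adding site to the minimization is optional, given the reported limit on factors, and the model term does not depend on it.

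The cost is one model term and no new data. If there is no site difference and allocation is pooled, it is about 0.3 points of power, roughly 1 of 128 participants.

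Separately, reconcile the allocation list in Human Subjects with those in Minimization Screen, Table 5 and limitations item 6, and make the model contain exactly the factors used in allocation. This needs only a text correction, plus a model term if time from diagnosis was in fact used.

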Fig. 2. Change in weight with diet and exercise is dependent on the intensity of the protocol. Subjects in the placebo arm of the DPP study

contrast, the DPP lifestyle group and FDPS had a more intense diet and exercise protocol and a greater mean % weight loss. IGTN subjects where the diet and exercise protocol were less intensely monitored than the DPP "lifestyle group", but more than the DPP "placebo" group, fall between these two groups.

[figure not shown]
Improvement in metabolic control with diet and exercise is associated with improvement in clinical, electrophysiological, and pathological measures of neuropathy. The improvements in metabolic function were associated with a trend toward improvement in neuropathy (Fig. 3-right). The greatest improvement was in the IENFD and QSART, measures of small nerve fiber function, whereas there was less change in NCS and other measures of large nerve fiber function. This supports the concept that small fibers are the first to recover in IGT associated neuropathy and that it may

take longer than 1 year for large fiber function to change. Small fiber and sensory subscores of the MDNS show the same change. In Fig. 3, changes on the right indicate improvement and left worsening. * = p<0.05. IENFD was measured from 3-mm skin biopsies at the distal leg and proximal thigh at baseline and after 1 year in subjects with IGT (See Appendix). Each received diet and exercise counseling as a standard of care. NCS, QSART, and the MDNS were performed, and a visual analog pain scale was completed. Baseline distal IENFD was 0.9+1.2 fibers/mm and proximal IENFD was 4.8+2.3 fibers/mm. Baseline distal IENFD correlated with fasting glucose (0.001) and OGTT (0.01). After 1 year of treatment, there was a 0.3+1.1-fiber/mm (30%) improvement in distal IENFD and a 1.4+2.3-fiber/mm (70%) improvement in proximal IENFD (0.004). There was a greater improvement in the proximal thigh because many participants had no distal skin fibers, but all had proximal fibers, thus proximal IENFD may be a better measure of early nerve regeneration. Proximal IENFD was used to power the IENFD endpoint in the current proposal. The change in proximal IENFD correlated with a change in sural sensory amplitude (0.03).

This data represents a mean of the whole natural history cohort and cannot separate out those participants who showed the greatest improvement in weight loss and exercise capacity. The current proposal will address this question.

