Sample size will be based on the previous data from our IGTN natural history study and relevant pilot data from our ongoing Rehab R&D-funded Merit Review T2DM exercise study. An assumption is that the IGTN study represents a more intense intervention than SC and that the difference between the TDPA and the SC will be at least as large as the difference between baseline and the 6 or 12 months endpoints of IGTN (see below). The table below uses the IGTN baseline-endpoint data to compute an adjusted standard deviation (i.e. the SD can be reduced by taking into account the contribution of each individual's baseline in explaining the overall variation). For the T2DM study, PA (from CHAMPS scores) is available at baseline (Mean \pm SD 1350.5 \pm 946.5) and at 10 weeks of a physical activity enhancement intervention for our pilot group (10 week delta=over 600). At present, we do not have sufficient 6 or 12 month data for PA in T2DM, but we anticipate that the initial PA benefit may be sustained. The expected sample size required is noted for two-sided alpha=0.05 and with power of 80%.

Study	Variable	SD of the outcome adjusted for baseline	Desired TDPA-SC difference	Effect size for adjusted outcome	Sample size per group
IGTN	6MW	97	50	0.51	64
IGTN	IENFD	2.2	1.0	0.45	53
T2DM	PA	1000	500	0.50	64

Thus, the sample size estimate needed for the primary hypothesis efficacy measure (6MW) will be 64 per group for a total of 128 needed in the study. In the T2DM CHAMPS PA data, using baseline information and assuming a delta of 500 and standard deviation of 1000, with 64 subjects per group we can detect an effect size of 0.5. Based on reliable data from the current IGTN study, we know that the actual 1 year dropout for enrolled subjects is 4%, so that the number of subjects to be enrolled is 133. We estimate a more liberal 10% dropout rate from

baseline to the 12 month endpoint, thereby requiring randomization at baseline of 142 in order to guarantee recruiting the necessary 128 participants.

The sample size estimate needed for the secondary hypothesis efficacy measure (IENFD) will be 53 per group for a total of 106 needed in the study. Using the 10% dropout rate from baseline to the 12 month endpoint, 117 would be required for randomization, well within the 142 planned to satisfy the requirements for 6MW noted above.

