1) Human Subjects Involvement and Characteristics: Patients with documented IGR will be entered in the study. All patients will have baseline HbA1c measurements between <8%. All participants will have mild neuropathy as described below. A total of 142 participants will be entered in equal proportions between the two groups (SC and TDPA) using a minimization procedure. The scheme will be prepared to achieve equal sample sizes for the two groups, for age, gender, BMI, time from diagnosis of IGR. Persons assessing diet, PA, mobility function and neuropathy progression will be blinded to group assignment.

This research topic is relevant to both women and men, and both will be included as they are recruited, approximately in proportion to their representation among older adults with T2DM. African-Americans will be recruited in proportion to their numbers among patients with T2DM, and if needed, emphasis on recruiting African-Americans will assure they are not underrepresented in the study. Other minorities will be recruited based on their percentage in Washtenaw County, the primary recruitment region (3% Asian American, and 2% Hispanic).

Table 6 indicates the distribution of patients in Baltimore County, Maryland where the Baltimore VAMC and the University of Maryland are located and in Washtenaw county where the Ann Arbor VAMC and University of Michigan Hospitals are located. The distribution of Black or African Americans in Baltimore county is twice the national average and in Baltimore is over five times the national average thus increasing recruitment of minorities from this population group. In contrast, the distribution of Asian/Pacific Islander and Native American or Alaskan Native is greater in Washtenaw county than in Baltimore, increasing recruitment of these population group in Michigan. Both site will relatively under recruit Hispanics, although the rate of growth of this group is now among the highest in the nation in the greater Baltimore area. The distribution of patients seen at the Baltimore VAMC and the Ann Arbor VAMC is similar to respective demographics listed below with the exception that the proportion of male to female patients is greater. T2DM is more common in blacks than in the general population, and as much as three times more prevalent in some groups of American Indians (20), thus we predict that we will recruit an increased number of minorities into the study.

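### On the plan's own inputs the IENFD endpoint needs 77 evaluable participants per arm, not 53, so the planned 142 gives about 72% power, not 80%

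*Combined protocol and SAP*

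**What the plan says.** Section C(1) Methodology, under the sample size heading, sets one rule for all three rows of its table: "The expected sample size required is noted for two-sided alpha=0.05 and with power of 80" percent. The IENFD row reads "IGTN IENFD 2.2 1.0 0.45 53"; these are the source study, the variable, the SD adjusted for baseline, the desired difference between arms, the effect size and the number per group. The text introducing the table explains why that SD is an adjusted one: "the SD can be reduced by taking into account the contribution of each individual's baseline in explaining the overall variation".

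The prose below the table repeats the result ("IENFD) will be 53 per group for a total of 106 needed in the study"), adds 10% dropout, and concludes: "117 would be required for randomization, well within the 142 planned to satisfy the requirements for 6MW noted above". The Human Subjects section confirms equal allocation: "A total of 142 participants will be entered in equal proportions between the two groups". The Background section says which biopsy site the calculation refers to: "Proximal IENFD was used to power the IENFD endpoint in the current proposal".

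**The concern.** At a fixed alpha and power, a smaller effect size needs more participants. In this table the effect sizes are 0.51 (six-minute walk), 0.50 (physical activity) and 0.45 (IENFD), and the numbers per group are 64, 64 and 53. The smallest effect has the smallest sample, which no single method applied to all three rows can produce.

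The 53 is carried into 106 evaluable and 117 randomised, and then into a plain assurance that 142 is enough for IENFD. IENFD is one of two secondary endpoints and the only neuropathy measure in the table. The Current Status section says the clinical score and nerve conduction studies would need a much larger study to serve as endpoints, so they cannot make up for a weak IENFD comparison. If readers believe the endpoint had 80% power for a 1.0 fibers/mm difference, they may give a null result more weight than it deserves.

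**Working it through.** **Inputs, all from the sample size section unless noted.** Two-sided alpha 0.05; power 80%; SD 2.2, already adjusted for baseline; difference 1.0; equal allocation (Human Subjects section); dropout 10%, with 4% observed in the earlier natural history study; 64 evaluable per group from 142 randomised. The planned test is the group term in a baseline-adjusted regression at 12 months (Hypothesis testing plan).

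**Method.** The normal approximation is n per group = 2 × (1.960 + 0.842)² × (SD/difference)² = 15.70 × (SD/difference)². The two-sample t-test gives a value about one higher.

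**The plan's other rows.**
- Physical activity, 500/1000 = 0.50: 15.70 × 4 = 62.8, so 63; the t-test gives 63.8, so 64. This reproduces the plan's figure.
- Six-minute walk, 50/97 = 0.515: the t-test gives 60.1, so 61. The stated 64 is adequate.

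**The IENFD row.**
- Effect size 1.0/2.2 = 0.4545, printed as 0.45. The row is consistent up to this column.
- Normal approximation: 15.70 × 2.2² = 15.70 × 4.84 = 76.0, so 76.
- t-test: 76.9, so **77 per group**. With the rounded 0.45 it is 78.5, so 79.
- The stated 53 is not reproduced.

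**Could another convention give 53?**

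| Variant | n per group |
|---|---|
| One-sided alpha 0.05 | 61 |
| Most favourable rounding of the inputs (1.05/2.15) | 67 |
| 2:1 allocation | 57 and 114 |
| Difference 1.2, SD 2.2 | 54 (53 by normal approximation) |
| SD about 1.82, difference 1.0 | 53 |
| Further baseline correlation of about 0.55 | 53 (normal approximation) |

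The first three keep the printed difference and SD, within rounding, and miss. The last three reach about 53 but depart from the stated inputs, and the last uses the baseline adjustment twice. A sample of 53 per group has 80% power at an effect size of 0.549, which is a difference of 0.549 × 2.2 = 1.21.

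**Number to randomise.** 2 × 77 = 154 evaluable; 154/0.9 = 171.1, so 172 at 10% dropout. The plan states 106 and 117. (106/0.9 is 117.8, so the 117 is also rounded down; this is minor.)

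**Power for a 1.0 difference with SD 2.2 (t-test).**

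| Evaluable per group | Scenario | Power |
|---|---|---|
| 53 | the plan's IENFD figure | 64% |
| 64 | 142 less 10% (142 × 0.9/2 = 63.9) | 72% |
| 68 | 142 less 4% (142 × 0.96/2 = 68.2) | 75% |
| 71 | 142, no dropout | 77% |
| 77 | required | 80% |

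With 64 per group, 80% power is reached at an effect size of 0.499, which is a difference of 0.499 × 2.2 = 1.10 fibers/mm.

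**The case against.** The strongest reply is that the documents do not show which cell is wrong. The 53, 106 and 117 recur in the prose, while the 1.0 and 0.45 stand only in the table row. If a difference of 1.2 was intended, 54 per group (108 evaluable, 108/0.9 = 120 randomised) is within 142, the assurance is true, and power at 64 per group is about 86%. This is possible. It requires two cells to be wrong, however, and those two agree with each other and with the SD (1.0/2.2 = 0.45). It stands as a reason for the sponsor to say which figure was intended.

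A second reply is that the expected effect may be larger than 1.0. The Background section reports a one-year proximal change of 1.4 (SD 2.3) in the earlier study, and the sample size section assumes the difference between arms will be at least as large as the change seen there. At 1.4, about 40 per group suffices with SD 2.2, and power at 64 per group is about 95% (93% with SD 2.3). That is useful context, but the plan chose 1.0 as the difference to detect, and its 80% claim must hold at 1.0. Nor does 1.4 explain 53.

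Third, the endpoint is secondary. The trial is sized on the six-minute walk, and the table error does not touch the analysis, the allocation or the primary inference. All of that is correct. It limits the consequence but does not make the stated figures right.

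**Conclusion.** The concern holds. On the inputs as tabulated, IENFD needs 77 evaluable per group (154 in total, 172 randomised at 10% dropout), against the stated 53, 106 and 117. The planned 142 does not deliver 80% power for a 1.0 fibers/mm difference under any dropout rate: power is about 72% at 10% dropout, 75% at 4% and 77% with none.

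These figures assume that the SD of 2.2 and the difference of 1.0 are what the sponsor meant, and that the test is two-sided at the full 0.05. The plan's section on multiple inferences mentions Bonferroni-type control; any reduction of alpha for IENFD would lower power further. The shortfall is moderate and concerns a secondary endpoint. The sizing for the six-minute walk stands.

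**What to change.** The sponsor should establish which figure in the IENFD row is wrong, and then do one of the following.

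- **If SD 2.2 and difference 1.0 were intended:** change the number per group to 77. Remove the statements that 53 per group (106 in total) are needed, that 117 randomised would be enough, and that the planned 142 covers this comfortably. State instead that with 142 randomised and 10% dropout, power for IENFD is about 72% for a difference of 1.0 fibers/mm and 80% for 1.1.
- **If a difference of about 1.2 was intended:** correct the difference to 1.2, the effect size to 0.55 and the number per group to 54. Give the reason for choosing 1.2, and restate the totals as 108 evaluable and 120 randomised.

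The cost is one table row and two sentences. No extra enrolment or procedures are needed. In the first case the stated power for a secondary endpoint becomes less favourable, and a null IENFD result should be read with that power in mind.
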